1. RATIONALE OF THE TRIAL

1.1.SOFT-TISSUE SARCOMAS

Soft tissue sarcoma (STS) is a rare malignant tumour arising in connective tissue of the extremities, the truncal wall or the retroperitoneal space. In France, its incidence is 3,6 cases per 100000 population per year (approximately, 4000 new cases are diagnosed each year in France) [1].

Surgery is the cornerstone of the management with radical resection or conservative resection followed by external beam radiotherapy. For locally advanced STS, when surgical resection is impossible, radiotherapy alone may be offered but local control and outcome are poor. Slater et al., reported in 72 patients with unresectable sarcomas treated with radiotherapy alone (44-88Gy) a 5-year local control of only 29% [2]. In another cohort of 112 patients, 5-year local control, disease free survival and overall survival were 45%, 24% and 35% respectively [3]. Slater's and Kepka's series seem showing a dose response relationship with longer tumour control in patients who received 65Gy or more but without statistical significance. Moreover, an increase of the delivered dose is difficult in practice with more complications. In Slater's series, 26% of patients treated with a dose above 65Gy had major complications. New directions must be also explored to improve radiotherapy efficacy in locally advanced STS.

1.2.OLAPARIB

Olaparib (AZD2281, KU-0059436) is a potent Polyadenosine 5'diphosphoribose [poly (ADP ribose) polymerisation (PARP) inhibitor (PARP-1, -2 and -3) that is being developed as an oral therapy, both as a monotherapy (including maintenance) and for combination with chemotherapy and other anti-cancer agents.

PARP enzymes are essential for repairing DNA single strand breaks (SSBs). Inhibiting PARPs leads to the persistence of SSBs, which are then converted to the more serious DNA double strand breaks (DSBs) during the process of DNA replication. During the process of cell division, DSBs can be efficiently repaired in normal cells by homologous recombination repair (HR).

The pre-clinical experience is fully described in the current version of the olaparib IB.

Olaparib has been tested in a standard range of safety pharmacology studies e.g. dog cardiovascular and respiratory function tests, and the rat Irwin test. There were no noticeable effects on the cardiovascular or respiratory parameters in the anaesthetized dog or any behavioural, autonomic or motor effects in the rat at the doses studied.

The toxicology studies indicate that the target organ of toxicity is the bone marrow.

Further information can be found in the current version of the olaparib IB.

1.2.1. Clinical experience

Clinical experience with olaparib is fully described in the current version of the olaparib IB.

A full description of the emerging safety profile for olaparib, with guidance for investigators, is provided in the IB.

1.3.STUDY RATIONALE

Multiple preclinical data demonstrate that PARP inhibition increases cytotoxicity and tumor growth delay in combination with ionizing radiation. The mechanisms of these radiosensitizing effects are well understood in vitro but are less clear in vivo.

The cytotoxic effects of radiotherapy are mediated by DNA damages: SSBs, DSBs at a ratio of 25:1. SSBs are not directly cytotoxic but during DNA replication may generate potentially lethal DSBs by collapse of stalled replication forks. Radiation-induced SSBs are primarily repaired by base excision repair of which PARP-1 is a key component. Inhibition of PARP increases also sensitivity to ionizing radiation in cells.

Preclinical in vitro studies

The study of PARP-1 as a potential molecular target in cancer therapy began in the 1980s. Early studies revealed that inhibition of PARP led to radiosensitization of mammalian cells [4]. Subsequently, cells with genetic delation of PARP-1 were shown to be more sensitive to ionizing radiation than cells with fonctionnal PARP-1 [5]. Additional studies have demonstrated radiosensitization by a variety of PARP inhibitors in multiple cell line models with dose-enhancement ratios of 1.3-1.7 [6-10]. In some studies, PARP inhibitors selectively radiosensitize actively replicating S-phase cells [11] and it is proposed that

the mechanism by which PARP inhibition increases ionizing radiation sensitivity is by inhibiting the repair of SSBs that convert to DSBs upon collision with replication forks in S-phase [12]. Such lesions can be visualized by persistence of ionizing radiation-induced γ H2AX foci following PARP inhibitor treatment [8, 9]. These data were supported by the observation that PARP inhibition increased the γ H2AX foci and RAD51 foci [13]. However, PARP has also been implicated in DSBs repair through interaction with non-homologous end joining (NHEJ) and has been shown to exist in a complex with DNA-PKcs and Ku70/80, that are important components of the NHEJ pathway [14, 15].

Preclinical in vivo studies

Some studies have demonstrated better in vivo radiosensitization by PARP inhibitors than expected by in vitro studies. In mice bearing SCC7, RIF-1, KHT sarcomas and Ewing sarcomas, PARP inhibitor caused an up to 3 fold enhancement of the therapeutic effect of X-rays [16,29]. In combination with fractionated X-rays PARP inhibitor doubled the tumor growth delay in mice bearing LoVo xenografts [17] and orally administered PARP inhibitor prior to irradiation significantly enhanced the irradiation-induced growth inhibition in HNSCC xenografts [18]. Many preclinical studies have been shown significant increase of the anti-tumor activity of ionizing radiation xenograft models of human colon, lung, prostate, breast cancers and gliomas [9, 19–23]. Olaparib in combination with radiotherapy caused significant tumor regression of Calu-6 NSCL carcinoma xenografts when compared to radiotherapy alone [24].

One explanation to these good in vivo results could be the enhancement of tumor vascularization and oxygenation by PARP inhibitors by vasoactive properties of these molecules. Indeed, oxygen is a key component of the radiation-induced DNA damages with hypoxia inducing radioresistance. Studies revealed that PARP inhibitor also increased the transient perfusion of the tumors [17]. Further investigations revealed that PARP inhibitors cause vasodilatation of pre-constricted rat arteries ex vivo and improved vascular perfusion of tumors in vivo [25, 26]. Olaparib was also demonstrated to have vasoactive effects ex vivo and in vivo and enhanced the antitumor activity against human NSCLC xenografts [24].

Clinical studies

As a consequence of these collective preclinical data, ongoing phase 1 clinical trials assess the combination of PARP-1 inhibitors with radiotherapy. However, no trial focus on radiotherapy of STS.

1.4.BENEFIT/RISK AND ETHICAL ASSESSMENT

Some clinical trials (phase 1 trials essentially) are ongoing to explore the role of PARP inhibitors in combination with radiotherapy but no final results are available. Only, an interim report of a phase I trial testing a PARP inhibitor in combination with whole brain radiotherapy showed a good tolerance of the combination and further dose escalation is planned [27]. Elsewhere, a recent study shows that the radiosensitizing effects can be observed at much lower Olaparib doses than the single agent effects [28]. Previous clinical studies showed that as single agent Olaparib was well tolerated with maximal tolerated dose for monotherapy at bi-daily 400mg capsules. Also it can be expected that lower Olaparib doses delivered in combination with radiotherapy were safe and sufficient to increase radiosensitivity and efficacy of radiotherapy.

2. OBJECTIVES

2.1.PRIMARY OBJECTIVE

2.1.1. Dose escalation

To establish the recommended phase II dose (RP2D), the maximum tolerated dose (MTD), the safety profile and the dose limiting toxicities (DLT) of Olaparib given with concomitant radiotherapy in patients with locally advanced/unresectable soft-tissue sarcoma.

2.1.2. Expansion cohort

To determine preliminary signs of anti-tumor activity of Olaparib given with concomitant radiotherapy in patients with locally advanced/unresectable soft-tissue sarcoma in terms of 6-month non-progression (complete response, partial response, stable disease as per RECIST v1.1) after centralized radiological review.

2.2.SECONDARY OBJECTIVES

2.2.1. Dose escalation

- Preliminary signs of anti-tumor activity of Olaparib given with concomitant radiotherapy in terms of 6-month non-progression, 6-month objective response, objective response under treatment, best response under treatment, 1-year progression-free survival (PFS) and 1-year overall survival (OS). Subgroup analyses will be conducted for metastatic and non-metastatic patients.
- Functional assessment before and after treatment using the Muskuloskeletal Tumor Society functional form (MSTS ; Enneking et al. Clin Orthop 1993).
- Pharmacokinetics (PK) of Olaparib.

2.2.2. Expansion cohort

- Preliminary signs of anti-tumor activity of Olaparib given with concomitant radiotherapy in terms of 6-month objective response, objective response under treatment, best response under treatment, 1-year progression-free survival (PFS) and 1-year overall survival (OS). Subgroup analyses will be conducted for metastatic and non-metastatic patients.
- Toxicity profile of Olaparib given with concomitant radiotherapy.
- Pharmacokinetics (PK) of Olaparib.
- Functional assessment before and after treatment using the Muskuloskeletal Tumor Society functional form (MSTS; Enneking et al. Clin Orthop 1993).
- Pharmacodynamics (translational research): Prognostic markers of anti-tumor activity of Olaparib given with concomitant radiotherapy will be investigated.

3. STUDY DESIGN

3.1.OVERALL STUDY DESIGN

This is a multicenter, prospective phase Ib trial based on a dose escalation study design assessing four dose levels of Olaparib given with concomitant radiotherapy, followed by an expansion cohort once the recommended phase II dose (RP2D) has been established.

3.2.RATIONALE FOR STUDY DESIGN AND DOSES

Few clinical data about combination of Olaparib and radiotherapy are available and more or less about Olaparib and STS radiotherapy. Therefore, a phase 1 dose escalation trial has been designed in order to determine the MTD and the safety of the combination. An expansion cohort should allow to appreciate anti-tumor activity of the combination.

Study population was defined as patients with locally advanced/unresectable STS (with or without metastases) because their outcome with radiotherapy alone is very poor.

The choice of olaparib doses was based on preclinical data showing that low doses are sufficient with radiotherapy.

3.3.DEFINITIONS

Dose-limiting toxicity (DLT)

A DLT is defined as an adverse event (AE) or laboratory abnormality that fulfills all the criteria below:

- Occurs during the period of observation of DLTs defined as the period between the first day of treatment administration and up to 6 weeks after the end of radiotherapy.
- Is considered to be at least possibly related to the treatment strategy (radiotherapy or Olaparib).
- Is unrelated to disease, disease progression, inter-current illness, or concomitant medications.
- Meets one of the criteria below, graded as outlined or according to NCI CTCAEv4.0:
 - Any grade ≥ 3 musculoskeletal or cutaneous toxicity within the field of radiation:
 - Occurring at a radiotherapy dose $< 30\text{Gy}$
 - Occuring at a radiotherapy dose $\geq 30\text{Gy}$ and without regress to a grade ≤ 2 in a time limit of 4 weeks
 - Any non-hematological toxicity \geq grade 3 (except for nausea, vomiting, fatigue, alopecia and fever)
 - Laboratory abnormality \geq grade 3 lasting > 5 days (except for lymphopenia, hyperglycaemia and changes in serum electrolytes/enzymes without clinical impact)

- Febrile neutropenia (absolute neutrophil count [ANC] < 1.0 x10⁹/L and fever ≥ 38.5°C) and/or documented infection with ANC < 1.0 x 10⁹/L
- Grade 4 neutropenia (absolute neutrophil count < 500) lasting ≥ 7 days
- Grade 4 thrombocytopenia or bleeding requiring a platelet transfusion
- Any other toxicity grade ≥ 4
- Any other study drug related toxicity considered significant enough to be qualified as DLT in the opinion of the investigators after discussion with the sponsor.

In addition, the following events, in case they are related to the toxicity of the treatments, will also be considered as DLT:

- Interruption of radiotherapy for seven consecutive days or longer,
- Interruption of Olaparib for 14 days or longer, whether this interruption happens on consecutive days or not.

A **DLT validation committee** will be consulted before the first escalation to a new dose level (see section 12.1.2).

Maximum tolerated dose (MTD)

The MTD for Olaparib is defined as the dose at which an unacceptable frequency of DLT is observed (33%). Conclusions of the steering committee for the definition of the MTD will be submitted to an independent committee (IDMC) before opening the expansion cohort.

Recommended phase II dose (RP2D)

The RP2D dose corresponds to the dose level to be recommended for further investigations in phase II trials. The RP2D dose for Olaparib will be identified by the steering committee based on the MTD for Olaparib as defined following the dose escalation trial, as well as additional safety data, including acute and late toxicities, PK and PD data. Data from all patients (dose escalation trial and expansion cohort) will be used to define the RP2D.

3.4.DOSE ESCALATION PART

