7.2.5. Adverse effects management

Acute toxicities of radiotherapy of STS are essentially musculoskeletal or cutaneous toxicities. They will be evaluated through a clinical examination performed each week during radiotherapy and one month after the end of radiotherapy (D8, D15, D22, D29, D36, D43, D50, D64, D78, D92) or until regression of a grade 3. Grading of adverse events will be done according to the CTCAE v.4.

- If a grade ≥ 3 musculoskeletal or cutaneous toxicity is observed before a radiotherapy dose of 30Gy, Olaparib and radiotherapy were stopped (DLT) but radiotherapy could be continued when regression to a grade ≤ 2 will be achieved.
- If a grade ≥ 3 musculoskeletal or cutaneous toxicity is observed after a radiotherapy dose of 30Gy, radiotherapy will be stopped until regression to a grade ≤ 2 and then will be continued. Olaparib will be continued during radiotherapy interruption. If grade ≥ 3 persits more than 4 weeks, Olaparib will be stopped (DLT).

The irradiated skin area that will be included in the operative volume must be identified during contouring and protected during planification (ALARA) in order to limit the occurrence of post-operative acute cutaneous and mucous complications [30 - 31].

7.3.ASSOCIATED TREATMENT: SURGERY FOR RESECTABLE DISEASE

Surgery will be performed by expert surgeon within 12 weeks of radiotherapy completion in reference centers labelled by the French NCI and NETSARC network.

Post-operative complications will be recorded up to 12 months after surgical complication.

Surgical sample will be analyzed to determine histological response and data will be collected in case report form.

The decision of surgery has to be taken by the investigational site during Multidisciplinary Tumor Board (RCP),

The decision of surgery has to be notified to the sponsor as soon as possible (i.e. before surgery).

Post-surgery clinical exam: addition of 3 visits after surgery (D30, D60 and D90). The next visits remain unchanged (follow-up every 3 months).

Post-surgery complications grade 3 should be reported immediately as serious adverse event to the Vigilance Unit of the Sponsor.

CONFIDENTIAL

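### The general grade ≥3 non-haematological DLT criterion does not except in-field skin and musculoskeletal events, so read literally it cancels their 4-week regression allowance at ≥30 Gy

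*Protocol*

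**What the plan says.** Protocol section 3.3 defines a DLT through timing and causality conditions plus a list of toxicity criteria. An event qualifies if it "Meets one of the criteria below, graded as outlined or according to NCI CTCAEv4.0", so the criteria are alternatives. Three provisions bear on the same event.

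- **In-field criterion (3.3).** Grade ≥3 "musculoskeletal or cutaneous toxicity within the field of radiation" is a DLT if it occurs below 30 Gy. At 30 Gy or more it is a DLT only if it does not regress to grade ≤2 "in a time limit of 4 weeks".
- **General criterion (3.3, the next item).** Any non-haematological toxicity of grade ≥3 is a DLT, "except for nausea, vomiting, fatigue, alopecia and fever".
- **Interruption rule (3.3, after the list).** "Interruption of radiotherapy for seven consecutive days or longer" also counts as a DLT when it is due to treatment toxicity.

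The synopsis and SAP section 1.1 repeat all three.

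Section 7.2.5 says how to manage the event. After 30 Gy, "radiotherapy will be stopped until regression to a grade" of 2 or less, and "Olaparib will be continued during radiotherapy interruption". Only if grade ≥3 "persits more than 4 weeks, Olaparib will be stopped (DLT") does that section call it a DLT. For events before 30 Gy it applies the DLT label at once.

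**The concern.** Every in-field skin or musculoskeletal event of grade ≥3 is also a non-haematological toxicity of grade ≥3. Because one criterion is enough and the general one has no exception for in-field events, it captures all of them at onset. The 30 Gy split and the 4-week allowance then have nothing left to decide. Two later catch-all items in the same list are limited to other toxicities; the general criterion is not.

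Section 7.2.5 plainly intends the allowance to operate, since it keeps olaparib going while the event is open. A site working from 3.3 and a site working from 7.2.5 can therefore report the same event differently.

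DLT incidence per dose level is a primary endpoint (section 9.1). The first DLT moves allocation from the 3+3 scheme to TITE-CRM (section 3.4.2). DLT status also feeds the final posterior toxicity estimates (section 10.3). Section 7.2.5 describes the acute toxicity of this radiotherapy as essentially cutaneous and musculoskeletal, so the gap falls on the class of event most expected here.

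**Working it through.** **1. Calendar.** Inputs from section 3.4.1: 33 fractions of 1.8 Gy, Monday to Friday, from D8; DLT window of 13.5 weeks.

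- 33 × 1.8 = 59.4 Gy, as stated.
- Counting weekdays from D8, the last fraction falls on D52 (D54 if D8 is a Thursday or Friday). The stated window is reproduced: 7.5 + 6 = 13.5 weeks, and by calendar D52 + 42 = D94, which is 13.4 weeks.
- 16 × 1.8 = 28.8 Gy and 17 × 1.8 = 30.6 Gy, so 30 Gy is first passed at fraction 17, on D30 (D32 for a Friday start).

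For an unresolved event starting on D30, the general criterion gives a DLT on D30, the interruption rule on D30 + 7 = D37, and the in-field criterion on D30 + 28 = D58.

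**2. Which events change status.** The table takes a grade ≥3 in-field event at ≥30 Gy and assumes that radiotherapy is held for exactly as long as the event stays at grade ≥3.

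| Course of the event | General criterion | In-field criterion and 7.2.5 | 7-day interruption rule | Does DLT status depend on the reading? |
|---|---|---|---|---|
| During radiotherapy, regresses in under 7 days | DLT at onset | Not a DLT | Not a DLT | **Yes** |
| During radiotherapy, regresses between day 7 and week 4 | DLT at onset | Not a DLT | DLT at day 7 | No under 3.3 as a whole; 7.2.5 read alone suggests no DLT |
| During radiotherapy, not regressed by week 4 | DLT at onset | DLT at week 4 | DLT at day 7 | No, only its date |
| After the last fraction, regresses within 4 weeks | DLT at onset | Not a DLT | Does not apply | **Yes** |
| After the last fraction, not regressed by week 4 | DLT at onset | DLT at week 4 | Does not apply | No, only its date |

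Two rows depend on the general criterion alone. The second row is settled by 3.3, but a reader of 7.2.5 would not know it.

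**3. Whether another text sets precedence.** SAP sections 2.1.1 and 3.2.1.1 take DLTs from the form flags DLT_RA and DLT_ON and do not derive them from grade, dose and dates. SAP section 4.2.9 lists Table 9.2 (in-field) and Table 9.3 (general) without saying which one an in-field event belongs to. Protocol section 12.1.2 sets up a DLT validation committee but gives it no rule for this case.

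**4. Size.** One event coded the other way changes a three-patient level from 0/3 to 1/3 = 33%, against a target of 33%. At an average level of 24/4 = 6 patients it changes the observed rate by 1/6 = 17 points.

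The documents give no rate for the affected events. As an assumption only, let q be the proportion of patients with an event that is a DLT under the general criterion alone:

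| q (assumed) | Chance of at least one in 3 patients, 1 − (1 − q)³ | Expected in 24 patients, 24q |
|---|---|---|
| 2% | 6% | 0.5 |
| 5% | 14% | 1.2 |
| 10% | 27% | 2.4 |
| 20% | 49% | 4.8 |

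The range shows how the result scales. It is not evidence that any of these rates applies.

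**The case against.** **The specific criterion governs.** A reading that leaves one item of a list without effect is normally rejected, and 7.2.5 shows the intent. This is probably what the authors meant, and the fix adopts it. But no text states it, and a rule on which a primary endpoint depends should not have to be inferred from a management section.

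**The interruption rule does not contradict the in-field criterion.** This stands. Section 3.3 introduces the rule as an additional route to a DLT. A reader might infer three competing definitions of the same event, but only the overlap of the general and in-field criteria is a conflict. The fault in 7.2.5 is one of omission.

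**DLT coding is reviewed centrally.** This stands in part. The protocol consults the committee before the first escalation to each new level, and SAP section 1.1 has it validate each notified DLT. It would be wrong to say that site coding enters the analysis unreviewed. Yet validating notified DLTs need not reach an event that a site following 7.2.5 never notified, and the committee has no precedence rule to apply.

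**Escalation gates.** A reader might go further and infer that, because an event can stay open for four weeks, the 6- and 8-week follow-up requirements allow unsafe escalation. The documents do not support that as a fault. Escalating on incomplete windows is how TITE-CRM works, and the committee is consulted before each first escalation. At the planned pace few events could be open: 56 × 30.44 / 41 = 41.6 days per patient puts the second patient at about D84 when the fourth is registered, so only onsets from D57 would be unsettled. Whether to exclude such patients from the count is a design preference. The dose-reduction table in section 7.1.6.2 already shows 100 mg b.i.d. as the RP2D, which suggests that escalation is complete.

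**Conclusion.** The point holds as a drafting conflict in the DLT definition. Taken literally, the general criterion makes every grade ≥3 in-field skin or musculoskeletal event at ≥30 Gy a DLT at onset and voids the 4-week allowance that 7.2.5 applies. The events whose status turns on this are those that regress in under seven days during radiotherapy and those that begin after the last fraction and regress within four weeks. Separately, 7.2.5 does not mention that its own radiotherapy hold becomes a DLT at seven consecutive days.

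One affected event is enough to take a three-patient level from 0/3 to 1/3 and, if it is the first DLT, to change the allocation method. How often this would happen is unknown. A reader might infer that the MTD is biased, but the documents give neither an event rate nor the prior and starting toxicity guesses of the dose-toxicity model, so no effect on the MTD can be claimed. If escalation has finished, classification still matters for the reported DLT incidence, the final posterior estimates and the refinement of the RP2D, which uses data from all patients.

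This is an inexpensive improvement, not a flaw that invalidates the design.

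**What to change.** 1. In section 3.3 and the synopsis, limit the general criterion to *other* non-haematological toxicity of grade ≥3. Add in-field musculoskeletal and cutaneous toxicity to its exceptions, stating that the preceding criterion judges it.
2. In section 7.2.5, state that a radiotherapy hold of seven or more consecutive days for such toxicity is a DLT under 3.3, even if the event later regresses within four weeks.
3. Carry the same wording into SAP section 1.1 and the titles of Tables 9.2 and 9.3, so that an in-field event is counted under the in-field criterion only.
4. Apply the rule to every escalation patient in the final DLT incidence and posterior analyses. This needs the radiotherapy dose at onset, the onset date and the date of return to grade ≤2. The adverse-event variables listed in SAP section 3.2.1.1 hold start and end dates with initial and maximum intensity, so the last date may have to come from the visit records.

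The cost is wording and a one-off check of the affected events. No visits are added, because 7.2.5 already follows grade 3 events until they regress. The downside is that short-lived in-field grade 3 events at ≥30 Gy no longer count as DLTs; they remain in the toxicity tables. The in-field criterion covers grade 4 as well, so if the sponsor wants a grade 4 in-field event to be a DLT at once, the new wording should say so.
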